2 EXHIBITS

Exhibit	Details
A	Case Report Forms
B	Informed Patient Consent
C	Study Logs
D	Surgical Technique
E	Radiographic Protocol
F	Rehabilitation Protocol
G	Intentionally left blank (Monitoring Procedures maintained at Sponsor)
H	Product Labeling
I	Investigators and IRB/Ethics Committee Information
J	Statement of Investigator
K	Device Product Codes
L	Anticipated Adverse Events
M	Implant Retrieval Procedure
N	Sample Financial Disclosure Form
O	Intentionally left blank (See Section 15.0 for Publication Information)
P	References

3 TABLE 1 STUDY SUMMARY

Title:	36 mm CERAMAX® Ceramic Hip System PMA POST-APPROVAL STUDY: Short to Mid-Term Follow-up of New Study Subjects
Short Title:	COC36 Post Approval Study-New Subjects
Treatment Device:	36 mm Delta CERAMAX® Ceramic-on-Ceramic Acetabular Cup Prosthesis System
Control Device:	None; this is a non-comparative study
Intended Use:	The Ceramic on Ceramic Hip System is indicated for primary, unilateral, cementless total hip replacement surgery in skeletally mature patients with non-inflammatory degenerative joint disease or any of its composite diagnoses of osteoarthritis, avascular necrosis and post-traumatic arthritis.
Objective:	This study is intended to gather short and mid-term information regarding the performance and safety of the commercially available 36 mm CERAMAX® Ceramic on Ceramic Total Hip System from a cohort of new study subjects that were not previously involved in the IDE study for this device. The compiled information will be included in the annual post-approval study (PAS) reports for the approved PMA (P070026).
Study Design:	A prospective, non-controlled, non-randomized, multicenter study. A minimum of 170 subjects will be prospectively enrolled into the study. Study sites will be comprised of both IDE study sites, as well as newly recruited sites. Subjects will be seen for a preoperative (pre-op) clinic visit at the time of consent, and then at 6-weeks, 1-year, 2-years, 3-years, 4-years and a minimum of 5-years postoperatively (post-op). If Subjects are not willing or able to return for a clinical and radiographic follow-up in the 3- and/or 4-year interval, then a telephone interview may be utilized for the purpose of determining device survivorship/patient satisfaction and case report form (CRF) 4b will be used. It is anticipated that a minimum of 136 unrevised subjects in this PAS will have a minimum 5-year post-op clinic evaluation.
Number of Sites:	Up to fifteen (15) sites will participate, consisting of up to 5 sites who participated in the IDE study and the remainder being newly recruited sites.
Subject Population:	Newly enrolled subjects at participating sites who meet the inclusion/exclusion criteria for this study.
Sample Size:	Sites will prospectively enroll a minimum of 170 new subjects into this PAS.

Title:	36 mm CERAMAX® Ceramic Hip System PMA POST-APPROVAL STUDY: Short to Mid-Term Follow-up of New Study Subjects
Study Duration:	
The anticipated duration of this investigation is approximately seven years from the time of study initiation given that
 
 • It may take up to a minimum of 2-years from the time of study initiation to enroll new subjects. • Each subject will be followed until they have completed their minimum 5-year follow-up. • The study will be closed when all subjects are at 5-years post-operatively.
Endpoints:	
Primary endpoint:
 
 • Device survivorship, which will be estimated with a Kaplan-Meier survivorship analysis at 5-years post-operatively. 
Secondary endpoints:
 
 • Device survivorship will also be estimated at each year post-operatively. • Harris Hip scores, Subject-hip outcomes, radiographic evaluation, and type and frequency of AEs will also be estimated at each year post-operatively.
Procedure Schedule:	Subjects will be assessed at the following intervals: pre-op, operative, 6-weeks, 1-year, 2-years, 3-years, 4-years, and a minimum of 5-years post-operatively.
Safety:	All adverse events (AEs) reported throughout the PAS will be summarized in annual study reports.

4 TABLE 2: SUBJECT MANAGEMENT STUDY SCHEDULE

Case Report Form (CRF) Number	Event / Visit	Pre-op		Operative	6 Wk	1 Yr	2 Yr	3 Yr	4 Yr	5 Yr Min
		-90 days of surgery	-180 days of surgery	Day 0	1–92 d	275-455 d	640-820 d	1,005-1,185 d	1,370-1,550 d	1,825–Section 9.10 d
N/A	Complete Screening Log	✓								
N/A	Obtain Informed Patient Consent (IPC)	✓								
N/A	Verify Inclusion / Exclusion Criteria	✓								
“STATUS”	Identify Protocol, Confirm Eligibility, Confirm Consent	✓								
1	Subject History	✓								
2	Harris Hip	✓			✓ [†]	✓	✓	✓	✓	✓
4a	Subject Hip Outcomes (Clinic)*					✓	✓	✓	✓	✓
4b	Subject Hip Outcomes (Phone)*							✓	✓	
6	Operative Details			✓						
7	Device Log			✓						
8	Interim Visit Report^{††}				✓	✓	✓	✓	✓	
9	Adverse Events**	✓			✓	✓	✓	✓	✓	✓
10	Withdrawal Form***	✓			✓	✓	✓	✓	✓	✓
Radiographs	Antero-Posterior (AP) ****		✓		✓	✓	✓	✓	✓	✓
	AP femur*****		✓		✓	✓	✓	✓	✓	✓
	Lateral		✓		✓	✓	✓	✓	✓	✓
	Cross-Table Lateral				✓					

[†] Range of motion is an **optional** assessment at the 6-week interval.

* If subjects are not willing or able to return for a clinical and radiographic follow-up visit in the 3- and/or 4-year interval, then a telephone interview may be utilized for the purpose of determining device survivorship/patient satisfaction and CRF 4b will be used.

^{††} To be completed, as applicable when subjects return for an unplanned visit (only between the protocol-defined windows).

** When applicable

*** The Withdrawal Form will be completed for **all subjects** either to document a premature withdrawal or to designate that the end of study/ 5-year final endpoint has been completed

**** For pre-op films **only**, the visit window can be -180 days before surgery

***** The AP femur view is required only when the distal end of the femur is not visible on the AP view

5 INTRODUCTION

The following information describes a post-approval study (PAS) to be conducted for the 36 mm DePuy Synthes CERAMAX® Ceramic Total Hip System with BIOLOX delta® advanced composite ceramic. This study is being conducted in accordance with *21 CFR Part 814, Subpart E- Post-approval Requirements* of the United States Code of Federal Regulations covering post-approval studies for premarket approval (PMA) applications approved by the Food and Drug Administration.

6 PURPOSE

This study is intended to gather short and mid-term information regarding the performance and safety of the commercially available 36 mm CERAMAX® Ceramic Hip System from a cohort of new study subjects that were not previously involved in the IDE for this device. The compiled information will be included in the interim and annual post-approval study reports for the approved PMA (PMA P070026) submitted to the FDA.

This is not a hypothesis driven study. Instead it is designed to estimate device survivorship with an anticipated margin of error.

7 DEVICE DESCRIPTION

A detailed listing of permitted product codes is included in **Exhibit D** (Surgical Technique, pages 40-46) and **Exhibit K** (Device Codes). A brief description of the permitted components is included in this section. Please note, the direct anterior surgical approach is not permitted in this protocol.

7.1 The 36 mm CERAMAX® Ceramic Hip System consists of:

- a modular 36 mm inner diameter ceramic bearing insert that secures to a titanium metal alloy PINNACLE™ Acetabular Shell via a taper locking mechanism; and
- a 36 mm outer diameter ceramic femoral head that is attached to a conventional femoral stem to complete the total hip prosthesis device configuration.

7.2 36 mm CERAMAX® Ceramic Acetabular Bearing Insert

The 36 mm ceramic acetabular bearing insert component is manufactured from high purity, dense alumina matrix composite ceramic. CCI

The insert is available in several inner diameter sizes, including 36 mm; only 36 mm inserts will be utilized in this PAS. The inserts secure to DePuy Synthes' PINNACLE acetabular shells by means of an interlocking mechanical taper. The PINNACLE Tamp Extractor can be used to reposition and or remove a ceramic PINNACLE insert that has not yet been seated. Instructions to use the Tamp Extractor are as noted in the **Exhibit D** (Surgical Technique, pages 34-35).

7.3 PINNACLE Metal Outer Shell

The shells are designed to assemble to the ceramic insert components described above. The styles utilized in this clinical investigation are the POROCOAT-coated PINNACLE 100, PINNACLE 300, Sector II, and Multi-Hole Series shells.

7.4 Ceramic Femoral Head

The 36 mm BIOLOX delta® ceramic femoral head components are manufactured from the same ceramic material as the acetabular bearing insert components. The femoral head is secured to the femoral stem component with an interlocking taper. There are two taper sizes: 11/13 and 12/14 and these sizes correspond to the appropriate femoral stem. The femoral head is available in several outer diameter sizes and multiple offsets; only 36 mm heads will be utilized in this PAS to match the inner diameter of the ceramic bearing insert.

7.5 Femoral Stem

The stems with the 36 mm CERAMAX® device include the SUMMIT® POROCOAT®, Tri-Lock® Bone Preservation Stem (BPS) and the S-ROM® devices only. Refer to **Exhibit K** for a complete listing of permitted stems.

8 STUDY DESIGN, IRB REVIEW, INFORMED PATIENT CONSENT (IPC), FINANCIAL DISCLOSURE

8.1 Study Design

This is a prospective, non-controlled, non-randomized, multicenter study of the 36 mm Ceramic on Ceramic (COC) device.

A new enrollment cohort of a minimum of 170 subjects will be prospectively enrolled into the study. Study sites will be comprised of both IDE study sites, as well as newly recruited sites. These subjects will be seen for a pre-op clinic visit at the time of consent, and then at 6 weeks, 1 year, 2 years, 3 years, 4 years, and a minimum of 5 years. The purpose of the pre-op visit will be to obtain patient medical history and baseline information. At the post-op clinic visits the following information will be obtained: a Harris Hip evaluation, radiographic evaluation, subject evaluation and adverse event information (if applicable). The primary endpoint in this study is device survivorship at 5 years post-op. A minimum of 80% of enrolled subjects will be confirmed to either have a surviving implant or to have had a revision at a minimum of 5 years post-op with a clinical evaluation.

For a given Subject, their study participation will end if they withdraw consent, as per PI decision, undergo a revision of either the acetabular shell and/or liner, are reported as deceased or when they have reached the final endpoint at 5 years.

8.2 Primary Endpoint

Device survival at 5 years post-op is the primary endpoint in this study. A revision is defined as the removal of any THA component(s), and device survival is defined as the lack of revision. A 5-year Kaplan-Meier survivorship estimate of COC 36 mm implanted hips will be estimated.

8.3 Primary Endpoint Justification

The maximum acceptable hazard of revision for the COC 36 mm system is assumed to be a constant 1% per year, that is, $h(t) = 0.01$. The survival function for this hazard is

$$S(t) = \exp \left[- \int_0^t h(u) du \right] = \exp (-0.01t),$$

so at 5 years, a minimally acceptable level of survival is assumed to be

$$S(10) = \exp[-0.05] = 0.951.$$

It will be demonstrated that the Kaplan-Meier 5-year point estimate of survival is at, or higher than this minimally acceptable level of 95.1%.

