8.4 Sample Size

The sample size will be a minimum of 170 prospectively enrolled subjects. This sample size will provide data upon which to obtain a 5-year survivorship estimate from newly enrolled subjects who did not participate in the COC36 IDE study. The sample size of 170 subjects in this PAS is approximately the same sample size of COC36 IDE investigational subjects, and hence will provide sufficient data on a new cohort of subjects to further support mid-term clinical success.

The objective of this study is to obtain an estimate of device survivorship at 5-years post-operatively. The enrolled 170 enrolled subjects will provide a minimum of 136 subjects (80% of enrolled subjects) with 5-year follow-up. This will yield a 5-year survivorship estimate that has an approximate 3.6% margin of error. In particular, Peto's estimate¹ for the variance of a Kaplan-Meier survival estimate is

$$\text{var}(\hat{S}(t)) = \frac{(\hat{S}(t))^2(1 - \hat{S}(t))}{n(t)}$$

where $\hat{S}(t)$ is the estimate of survival at time t and $n(t)$ is the number of unrevised subjects at risk (still being followed) at time, and t . Hence, if it is assumed that the point estimate of survival is at a minimally acceptable level of 95.1% for subjects in this PAS, and there is a minimum of 136 subjects (80% of enrolled subjects) at 5-years post-operatively upon which this estimate is based, then an estimate for the variance of the Kaplan-Meier survival estimate at 5 years is

$$\text{var}[\hat{S}(5)] = \frac{[0.951]^2(0.049)}{136} = 0.00034,$$

and a two-sided 95% confidence interval margin of error for survival at 5 years is anticipated to be approximately $1.96 * \sqrt{0.00034} = 3.6\%$.

A sample size of 170 enrolled subjects is therefore justified in order to obtain a 3.6% margin of error on a 5 year survivorship estimate.

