8.9 Analysis Plan

At the time of each interim PAS report, the following analyses will be presented for all subjects combined, as well as separately for each individual stem type that is represented in the PAS, and also separately for each individual cup type that is represented in the PAS:

- Baseline summary statistics will be calculated for age, weight, BMI, race, ethnicity and pre-op Harris Hip Scores for both cohorts. The proportion of each gender will be calculated.
- Harris Hip score summary statistics and change from baseline statistics will be reported for each protocol defined post-op visit interval. These will be provided for total Harris Hip score as well as the Harris Hip sub-scores (pain, function, activity, deformity, and range of motion). These will be provided for total Harris Hip score as well as the Harris Hip sub-scores. Results will be presented overall, as well as stratified by obesity (non-obese vs. obese) according to BMI (subjects with $BMI < 30$ and with $BMI \geq 30$, respectively)².
- Subject-reported outcomes will be reported for each protocol defined post-op visit interval.
- Radiographic analysis will be reported for each protocol defined post-op visit interval.
- Tabular displays of all cumulative reported adverse events will be provided by adverse event, as well as by category (intraoperative, postoperative-operative site, systemic, and overall). Tables will also be provided of adverse events over time.
- A Kaplan-Meier survivorship analysis will be provided, with device survivorship as a function of post-op time. A proportional hazards model will be provided, in which device survivorship is a function of post-op time, and with BMI (at the time of index surgery) as a covariate. Implant survival will be reported over time where greater than 40 hips are still at risk of revision.
- For Subjects that are not able to return to clinic at the 3- or 4-year interval, device survivorship information will be obtained through telephone interviews and will be utilized in the Kaplan-Meier analysis of device survivorship for the primary endpoint analysis in the study.

² Obesity is defined as $BMI \geq 30$ According to the World Health Organization:

<http://www.who.int/mediacentre/factsheets/fs311/en/>

Confidential
May 11, 2020

DePuy Synthes
CIP#12017 Revision D

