	8.9 Additional Endpoint Analyses	10
9	Data Monitoring Committee (DMC)	10
10	Appendix: Tables, Listings and Graphs Shells	11
11	Reference(s)	11

1 Study Design

This is a prospective, non-controlled, non-randomized, multicenter study of the 36 mm Ceramic on Ceramic (COC) device.

A new enrollment cohort of a minimum of 170 subjects will be prospectively enrolled into the study. Study sites will be comprised of both IDE study sites, as well as newly recruited sites. These subjects will be seen for a pre-op clinic visit at the time of consent, and then at 6 weeks, 1 year, 2 years, 3 years, 4 years, and a minimum of 5 years. The purpose of the pre-op visit will be to obtain patient medical history and baseline information. At the post-op clinic visits the following information will be obtained: a Harris Hip evaluation, radiographic evaluation, subject evaluation and adverse event information (if applicable). The primary endpoint in this study is device survivorship at 5 years post-op. A minimum of 80% of enrolled subjects will be confirmed to either have a surviving implant or to have had a revision at a minimum of 5 years post-op with a clinical evaluation.

For a given Subject, their study participation will end if they withdraw consent, as per Principle Investigator (PI) decision, undergo a revision of either the acetabular shell and/or liner, are reported as deceased or when they have reached the final endpoint at 5 years.

2 Treatment Assignment

Treatment assignment in this study was not randomized. All subjects received the 36mm COC device, and this was the only device configuration of interest in this PAS. Details regarding sample size are presented in Section 8.

3 Randomization and Blinding Procedures

This was a non-randomized, open-label study, and the sponsor was not blinded to any part of the study or data at any time during the study.

4 Interval Windows

The study includes the following time periods: Pre-op, 6 Wk, 1 Yr, 2 Yr, 3 Yr, 4 Yr, and 5 Yr Min. Intervals related to each are shown in Table 4-1 below.

Table 4-1 Interval Windows for Study Visits

Visit	Mininum Day	Maximum Day
Pre-op	-90 (-180 for Radiographic Data)	0
6 Weeks (Optional)	1	92
1 Yr	275	455
2 Yr	640	820
3 Yr	1005	1185
4 Yr	1370	1550
5 Yr Min	1825	2555

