Time point specific data which were collected for the primary and secondary efficacy-related objectives will be assessed for compliance with these intervals. Only data which can be attributed to the Visit intervals in Table 4-1 will be used in the analysis of primary and secondary endpoints. If multiple measurements fall into the specified windows, the last value within the window will be utilized for analysis.

5 Levels of Significance

There are no pre-specified hypotheses and all analyses are exploratory. Summaries of the primary and secondary endpoints in this study are being undertaken without established statistical power. Any p-values and confidence intervals which are provided are only intended to facilitate clinical judgement.

6 Analysis Sets

There is only one analysis set defined for this study:

Safety Analysis Set - Subjects are considered to be in this analysis set if they have provided informed consent and treated as indicated in the protocol.

All analyses will be conducted on the Safety Analysis Set.

7 Sample Size Justification

The sample size will be a minimum of 170 prospectively enrolled subjects. This sample size will provide data upon which to obtain a 5-year survivorship estimate from newly enrolled subjects who did not participate in the COC36 IDE study. The sample size of 170 subjects in this PAS is approximately the same sample size of COC36 IDE investigational subjects, and hence will provide sufficient data on a new cohort of subjects to further support mid-term clinical success.

The objective of this study is to obtain an estimate of device survivorship at 5-years post-operatively. The 170 enrolled subjects will provide a minimum of 136 subjects (80% of enrolled subjects) with 5-year follow-up. This will yield a 5-year survivorship estimate that has an approximate 3.6% margin of error. In particular, Peto's estimate¹ for the variance of a Kaplan-Meier survival estimate is

$$var(\hat{S}(t)) = \frac{(\hat{S}(t))^2(1 - \hat{S}(t))}{n(t)}$$

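### A 5-year point estimate at or above 95.1% cannot by itself demonstrate acceptable survival, and neither Protocol 8.9 nor SAP 8.5.2 commits to a confidence interval for that estimate

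*Protocol*

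**What the plan says.** Protocol 8.3 assumes a constant maximum acceptable hazard of 1% per year, derives exp(-0.05) = 0.951 as the lowest acceptable 5-year survival, and continues: "It will be demonstrated that the Kaplan-Meier 5-year point estimate of survival is at, or higher than this minimally acceptable level of 95.1" per cent. Only the point estimate is compared with that level.

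Elsewhere the study is presented as estimation. Protocol 6 says it is not driven by a hypothesis: "Instead it is designed to estimate device survivorship with an anticipated margin of error". Protocol 8.4 and SAP 7 give two reasons for 170 subjects. One is comparability with the earlier study: "The sample size of 170 subjects in this PAS is approximately the same sample size of COC36 IDE investigational subjects". The other is quantitative, a 3.6% "two-sided 95% confidence interval margin of error for survival at 5 years".

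The analysis sections do not carry that margin through. Protocol 8.9 states: "A Kaplan-Meier survivorship analysis will be provided, with device survivorship as a function of post-op time". SAP 8.5.2 makes the 5-year Kaplan-Meier estimate the primary analysis. Neither mentions an interval, a standard error or an interval method. SAP 5 says: "There are no pre-specified hypotheses and all analyses are exploratory", and: "Any p-values and confidence intervals which are provided are only intended to facilitate clinical judgement". SAP 8.4.2 merely permits intervals, and does so for secondary endpoints. By contrast, SAP 8.7 commits to exact binomial 95% intervals for adverse event percentages.

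**The concern.** The word *demonstrated* promises more than the comparison can deliver. A nearly unbiased estimate falls on either side of its true value about equally often. Clearing 95.1% therefore does not separate a device at the maximum acceptable hazard from one somewhat better or somewhat worse. A final report that followed Protocol 8.3 literally could call a device at the limit, or modestly beyond it, demonstrably acceptable.

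The interval is what would show the reader this uncertainty. It is also the quantity behind the numerical justification of the sample size, but the analysis text leaves it open. The method is not a formality either: near 95% survival with about 170 subjects, common methods give lower limits more than one percentage point apart. SAP 3 records that "the sponsor was not blinded to any part of the study or data at any time during the study", and SAP 8.5.1 says interim analyses of the primary endpoint were carried out. That is a reason to settle the method and the wording in writing before the final analysis.

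**Working it through.** **Inputs.** Maximum hazard 0.01 per year and the 95.1% level (Protocol 8.3); 170 enrolled, at least 136 (80%) with 5-year follow-up, and the printed Peto variance (Protocol 8.4, SAP 7). Assumptions of this review: constant hazards, and either no loss or 20% exponential, non-informative loss by year 5.

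**1. The plan's margin.** S²(1−S)/n = 0.951² × 0.049 / 136 = 0.000326, and 1.96 × √0.000326 = 3.5%. The printed variance of 0.00034 gives 1.96 × √0.00034 = 3.6%. The difference does not affect this point.

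**2. Chance of meeting 95.1% at the maximum hazard.** With complete follow-up, at most 8 revisions in 170 are allowed (162/170 = 95.3%; 161/170 = 94.7% fails), or at most 6 in 136 (130/136 = 95.6%; 129/136 = 94.9% fails). Binomial probabilities:

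| True 5-year revision risk | ≤ 8 of 170 | ≤ 6 of 136 |
|---|---|---|
| 0.049 (survival 95.1%) | 0.545 | 0.498 |
| 1 − exp(−0.05) = 0.0488 | 0.551 | 0.503 |

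Kaplan-Meier simulation, 170 subjects, 40,000 trials per setting:

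| True hazard per year | 0.5% | 0.75% | 1% | 1.25% | 1.5% | 2% |
|---|---|---|---|---|---|---|
| P(estimate ≥ 95.1%), 20% loss | 0.96 | 0.80 | 0.53 | 0.28 | 0.13 | 0.02 |
| P(estimate ≥ 95.1%), no loss | 0.97 | 0.82 | 0.55 | 0.29 | 0.13 | 0.02 |

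So the comparison is informative about a clearly poor device (2%) but not about one near the limit. A device better than the limit, at 0.75%, still misses about 2 times in 10.

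**3. What a result that just clears the level supports.** Take 8/170 with full follow-up: S = 0.9529.
- Symmetric: SE = √(0.9529 × 0.0471 / 170) = 0.01624; 0.9529 ± 1.96 × 0.01624 gives 92.1% to 98.5%. Peto and Greenwood coincide without loss.
- Log-log: the Greenwood sum is 8/(170 × 162) = 0.000290, with square root 0.01704; w = 1.96 × 0.01704 / |ln 0.9529| = 0.693. The limits S^exp(±w) are 90.8% and 97.6%.
- Exact binomial: 90.9% to 97.9%.

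The implied hazard at the lower limit is −ln(L)/5: 1.6% per year (symmetric), 1.9% (log-log) and 1.9% (exact). With 20% loss, simulated estimates of 95.1% to 95.6% had median lower limits of 91.9% (symmetric, Peto) and 90.6% (log-log).

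**4. Does the method matter?** Simulated coverage of true 5-year survival, counting trials with no revisions as misses for both methods:

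| Loss | Hazard per year | Symmetric (Peto) | Log-log (Greenwood) |
|---|---|---|---|
| 20% | 0.5% | 89.1% | 94.2% |
| 20% | 0.75% | 91.7% | 96.7% |
| 20% | 1% | 93.7% | 96.0% |
| 20% | 1.25% | 94.5% | 95.9% |
| 20% | 2% | 94.8% | 95.3% |
| None | 0.75% | 94.6% | 97.3% |
| None | 1% | 91.2% | 95.0% |
| None | 1.25% | 93.9% | 96.3% |

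Log-log stays at about 94 to 97%; symmetric ranges over about 89 to 95%. Log-log is not always nearer to 95%: with no loss at 0.75% per year the symmetric interval is closer. The symmetric interval can also pass 100%: at 3/170 its upper limit is 100.2%.

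**5. No revisions.** Neither Greenwood nor Peto gives a usable interval. The exact lower limit is 0.025^(1/n): 97.9% for n = 170 and 97.3% for n = 136. With this limit used in the zero-revision trials, log-log coverage at 0.5% per year and 20% loss becomes 96.3%.

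**The case against.** The half-the-time figure is close to a truism, since any nearly unbiased estimate behaves this way against its own true value. It would describe a defective test only if Protocol 8.3 were an inferential success rule. A reader might infer exactly that: a hypothesis test with an error rate near 50%. The documents do not support it. The sentence names the point estimate, sets no alpha and attaches no decision. Protocol 6, SAP 5 and SAP 8.4.1 all disclaim hypothesis testing. The later SAP does not repeat the sentence in the text available and uses 95.1% only as a planning value.

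A reader might also infer that no interval will be reported. That goes too far as well. The table shells are a separate document, and Protocol 14 ties the reports to an FDA guidance on presenting orthopaedic data; either may call for one. The planning text already gives a level, a sidedness and a variance formula, which suggests that an interval was intended.

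These arguments stand and limit the point; they do not remove it. The SAP neither withdraws the Protocol 8.3 sentence nor says how 95.1% is to be read in the final report. Intent to report an interval is not a commitment, and a planning variance is not a named analysis method. It is also fair to say that the choice of method is partly preference, and that fixing it after interim analyses have been seen gives only limited protection.

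**Conclusion.** The point holds as a minor one. The wording in Protocol 8.3 claims more than a point estimate can show, and the analysis sections leave the primary estimate without a committed interval or a named method.

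The size: a chance of about 50 to 55% of meeting the level for a device exactly at the maximum hazard, and a lower limit of about 91 to 92% for a result that just clears it. The binomial figures assume complete follow-up of 170 or 136 subjects. The simulated ones rest on constant hazards and, where loss is included, on the assumed 20% exponential loss. The finding on missing text covers only the sections available.

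Three stronger conclusions should not be drawn: that a hypothesis test has failed, that the sponsor has chosen or will choose a method to suit the data, or that the lower limit ought to exceed 95.1%. Nothing in the documents shows the first two. The third would bring a confirmatory criterion into a study declared to be estimation only.

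**What to change.** Add to SAP 8.5.2 text along these lines:

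> The 5-year Kaplan-Meier estimate will be reported with a two-sided 95% confidence interval (log-log transformation, Greenwood variance). If there are no revisions, an exact binomial lower limit based on the number at risk at 5 years will be given instead. Any comparison with 95.1% will be shown beside the interval. A point estimate at or above 95.1% will not by itself be described as demonstrating acceptable survival.

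Log-log is preferred because it stays within 0 to 100% and its simulated coverage was steadier. Another method would do if it is named before the final analysis. If the table shells already specify an interval, SAP 8.5.2 should state the same one. No lower-limit success criterion should be added. If Protocol 8.3 cannot be amended, the wording in the SAP and the final report is enough.

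The cost is a few sentences. Data, population, point estimate, sample size and the 95.1% level do not change. There are two downsides: a weaker claim if the estimate only just clears 95.1%, and a reported interval that will not exactly match the Peto-based planning margin.
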